## Treatment C (oral dosing):

The following blood PK samples will be collected in 2 mL EDTA K2 lavender top tubes:

- Week 1, Day 1: Pre-Dose, and at 1, 2, 3, 4, 6, 8, 12 and 24 h after oral administration (before Day 2 oral administration)
- Week 2: Day 8 Pre-Dose

- Week 3: Day 15 Pre-Dose
- Week 4: Day 22 Pre-Dose

The following blood PK samples will be collected in 4 mL EDTA K2 lavender top tubes

- Week 5: Day 29 Pre-Dose
- Week 5: Day 35 Pre-Dose, and 1, 2, 3, 4, 6, 8, 12 and 24 h after oral administration (the 24-h sample will be collected on Day 36).
- 8. Adhesion Assessments: **Treatment A and B** only To be performed prior to TDS removal and at specified timepoints. Adhesion assessments will be performed at 12, 24, 36, 48, 60, 72, 84, 96, 108, 120, 132, 144, 156, and 168 hour following TDS application. The 168-hour assessment will be conducted prior to the next TDS application. Adhesion assessments will be performed in all periods within ± 1 hour of scheduled assessment.
- 9. Irritation Assessments: Treatment A and B only The site receiving the TDS should be assessed for skin irritation prior to TDS application (if the score is greater than zero another site must be selected) for Period 1. For TDS applied in during period 2 or 3, the site receiving the TDS should be assessed prior to TDS application (if the score is greater than zero another site must be selected) and the previous week's TDS site should be assessed at 0.5, 24, 48 and 72 hours following TDS removal. If the score is greater than 1 at 72 hours, assessments are to be performed at the following time points until the score returns to ≤1: 120 and 168 hours post-removal and then every 3 days. For TDS applied in Week 5, the site receiving the TDS should be assessed prior to TDS application (if the score is greater than zero another site must be selected) and the previous week's TDS application (if the score is greater than 1 at 72 hours, assessments are to be performed at the following time points until the score returns to ≤1: 120 and 168 hours post-removal and then every 3 days. For TDS applied in Week 5, the site receiving the TDS should be assessed prior to TDS application (if the score is greater than zero another site must be selected) and the previous week's TDS site should be assessed at 0.5, 24, 48 and 72 hours following TDS removal.

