# 8. STUDY TREATMENTS

#### 8.1. Study Drug Treatments

On Day -1, eligible subjects will be checked into the research clinic to enter the Treatment Phase.

The study treatments are as follows:

**Treatment A (Test):** 5 mg/day Donepezil TDS manufactured with the commercial process applied weekly (within  $\pm 1$  hour of application time on Day 1) for 5 consecutive weeks (7-day wear each). All subjects will receive Treatment A in Period 1. The patch will be removed on the morning of Day 36.

At the start of Period 2, subjects will be randomized to one of the following treatments in Period 2. Subjects will receive the alternate treatment in Period 3. Randomization to the 2 treatment sequences will be stratified by gender.

**Treatment B (Test):** 10 mg/day CorplexTM Donepezil TDS manufactured with the commercial process applied weekly (within  $\pm 1$  hour of application time on Day 1) for 5 consecutive weeks (7-day wear each).

**Treatment C (Reference):** 10 mg Aricept® donepezil (1 x 10 mg/day tablet) administered QD for 35 consecutive days (within  $\pm 1$  hour of dosing time on Day 1). This is the Reference Listed Drug

(RLD).See Section 2 for a treatment phase schematic.

**TDS Application:** The first patch in each period with patch treatments (Treatment A or B) will be applied on Treatment Phase Days 1, 37, and 73. For patches #2 to #4, at the end of each week of patch wear (168 h after application), the worn patch will be removed and a new patch will be applied. The 168-h post-dose PK blood samples will be collected before removal of the worn patch.

The last (5th) patch in each period with patch treatments (Treatment A or B) will be removed after 168 hours of the last patch application, after the 168-h PK blood sample collection.

**Oral Dosing:** In periods with oral Aricept (Treatment C), a single dose will be administered daily on Treatment Phase Days 37-71 (Period 2) and 73-107 (Period 3).

**Drug-Free Days:** There is no study drug administration (neither patch wear nor oral dosing) on Treatment Phase Days 36, 72, and 108.

In each period wherein the treatment consists of a patch, the subjects will wear a total of 5 patches for a total of 35 days (5 weeks). The last (5th) patch in the period will be removed after the morning blood draw on Day 36 (168-hour time point). No treatment will be administered on Day 36 of the period; additional post-wear PK blood samples will be collected on Day 36 after any patch treatment.

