dose blood draw for Period 3 is collected. No treatment will be administered on Study Day 108. For the patch treatment in Period 3, the patch will be removed on Study Day 108 after the 168-hour blood sample collection.

• Follow-Up: 5 ±2 days after the day of the last oral drug administration or last TDS removal during the Treatment Phase, subjects will enter a Follow-Up Visit to evaluate safety parameters.

There will be no washout phase between treatment periods (with the exception of Day 36 within each period to collect post-treatment PK blood samples).

Subjects will participate in the study for up to 144 days, including up to 28 days of screening, a Treatment Phase with 3 treatment periods of 36 days each, and a 5 \pm 2 day Follow-Up Visit. Eligible subjects will stay in the research clinic for 109 days (108 overnight stays) during the Treatment Phase.

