2.3 Safety Objective

• To evaluate the safety and tolerability, including local skin tolerability (Dermal Response and Other Effects) of once-weekly Corplex[™] Donepezil TDS.

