6.11.1 Adverse Events

A treatment emergent adverse event (TEAE) is defined as:

- Any AE that has a new onset during the study between the initiation of study drug and the follow-up visit.
- Any pre-existing AE that has worsened in severity on or after the initiation of study drug till the follow-up visit.

The following rules will be used to assign a TEAE to a treatment:

- A TEAE will be assigned to the treatment received immediately before onset.
- Any TEAE reported within Period 1, Day 36, when no treatment is administered, will be attributed to the last treatment received before Day 36 began.
- If the severity of a TEAE increases in a later period the TEAE at the increased severity also will be assigned to the treatment received immediately before the increase in severity.

Page 33 of 61 Confidential

All TEAEs are defined as being definitely, probably, possibly related or unrelated to the study drug. If an AE has missing relationship it is assumed to be definitely related to the study drug for analysis purposes. Additionally, any SAE considered definitely, probably, or possibly related to the study drug will also be classified by the Sponsor as either "expected" or "unexpected" upon review by the medical monitor.

Adverse event severity will be graded as Grade 1: Mild, Grade 2: Moderate, or Grade 3: Severe or Medically Significant but not immediately life-threatening. Maximum severity will be assumed for an AE with missing severity.

All AEs will be coded using the most current version of the Medical Dictionary for Regulatory Activities (MedDRA version 23.1, updated to include activities related to COVID-19) by SOC and PT.

The following tables will be presented for AEs by treatment and overall using the Safety Population:

- Overall incidence and the number of AEs, SAEs, TEAEs leading to withdrawal.
- TEAE by system organ class and preferred term, incidence and number of events
- Treatment related TEAE by system organ class and preferred term, incidence and number of events
- Serious TEAE by system organ class and preferred term, incidence and number of events and "expected or unexpected" classification
- TEAE by system organ class and preferred term by nearest relationship to study drug, incidence and number of events
- TEAE by system organ class, preferred term and maximum severity, incidence
- TEAEs leading to early withdrawal by system organ class and preferred term, incidence

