14.3.1.8	Number (%) of Subjects with TEAEs associated	IP	
	with the TDS Application Sites Within the		
	General Disorders and Administration Site		
	Conditions by System Organ Class by Preferred		
	Term - Safety Analysis Population		
14.3.2	Listings of Deaths, Other Serious and		
	Significant Adverse Events		
14.3.2.1	Listing of Serious TEAEs – Safety Analysis	IP	
	Population		
14.3.2.2	Listing of Deaths – Safety Analysis Population	IP	
14.3.3	Narratives of Deaths, Other Serious and		
	Certain Other Significant Adverse Events		
14.3.4	Abnormal Laboratory Values		
14.3.5	Extent of Exposure, Dosage Information, and		
	Compliance		
14.3.5.1	Extent of Exposure – Safety Analysis Population	IP	
14.3.5.2	Protocol Deviations – Safety Analysis	IP	
	Population		
14.3.6	Vital Signs And Physical Examination		

Page 46 of 61 Confidential

Corium, Inc. CL-P-20003 Statistical Analysis Plan Version 2.0 Issue Date 15-JUL-2021

Table Number	Table Title	Validation Method	Shell Number (if repeat)
14.3.6.1	Vital Signs, Descriptive Statistics by Visit and Change from Baseline by Visit – Safety	IP	
1437	Analysis Population Othor Sofoty		
14.3.7	Hematology Data Descriptive Statistics by Visit	ID	
14.3.7.1	and Change from Baseline to Post-Dose Assessments – Safety Analysis Population	п	
14.3.7.2	Hematology Data, Normal Range Shifts – Safety Analysis Population	IP	
14.3.7.3	Serum Chemistry Data, Descriptive Statistics by Visit and Change from Baseline to Post-Dose Assessments – Safety Analysis Population	IP	14.3.7.1
14.3.7.4	Serum Chemistry Data, Normal Range Shifts – Safety Analysis Population	IP	14.3.7.2
14.3.7.5	Coagulation Data, Descriptive Statistics b Visit and Change from Baseline to Post-Dose Assessments – Safety Analysis Population	IP	14.3.7.1
14.3.7.6	Coagulation Data, Normal Range Shifts – Safety Analysis Population	IP	14.3.7.2
14.3.7.7	Urinalysis Data, Descriptive Statistics by Visit and Change from Baseline to Post-Dose Assessments – Safety Analysis Population	IP	14.3.7.1
14.3.7.8	Urinalysis Data, Normal Range Shifts – Safety Analysis Population	IP	14.3.7.2
14.3.7.9	12-Lead ECG, Descriptive Statistics by Visit and Change from Baseline to End of Treatment / Early Termination – Safety Analysis Population	IP	
14.3.7.10	12-Lead ECG, Overall Interpretation, Shift from Baseline to End of Treatment / Early Termination – Safety Analysis Population	IP	
14.3.7.11	Skin Tolerability Assessments, Dermal Response Scores – Skin Irritation Population	IP	

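### SAP 6.11.1 attributes adverse events by time alone, so an application-site reaction that first appears after a switch is counted under oral Aricept or, from the 5 mg to the 10 mg period, under the wrong TDS strength

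*SAP*

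**What the plan says.** The attribution rules are in SAP 6.11.1. The general rule is "A TEAE will be assigned to the treatment received immediately before onset". An event on the treatment-free Day 36 of Period 1 "will be attributed to the last treatment received before Day 36 began". The third rule deals with worsening: "If the severity of a TEAE increases in a later period the TEAE at the increased severity also will be assigned" to the treatment received just before the increase. The post-lock addendum changed the TEAE definition in this section but not these rules. Protocol 17.6 has no attribution rule of its own.

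On the calendar, SAP 1 says "There will be no washout phase between treatment periods", apart from the single Day 36 in each period. Protocol 8.1 adds: "There is no study drug administration (neither patch wear nor oral dosing) on Treatment Phase Days 36, 72, and 108". The fifth patch is removed on the morning of Day 36 or 72, and the next treatment starts on the morning of Day 37 or 73.

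Sites are scored 0.5, 24, 48 and 72 h after removal (SAP 6.2.9). If the score is still above 1 at 72 h, scoring continues at "120 and 168 hours post-removal and then every 3 days" (Protocol Section 1, footnote 9).

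SAP 6.11.1 presents the TEAE tables by treatment and overall. Table 14.3.1.8 is reserved for TEAEs associated "with the TDS Application Sites Within the" administration-site class.

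**The concern.** Oral tablets have no application site, yet the rule can place a patch-site reaction in the Aricept column. In sequence ABC it can also move a reaction caused by the 5 mg patch into the 10 mg column, where it looks plausible and is hard to notice. No section ties a local event to the patch that occupied the site.

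Local tolerability belongs to the safety objective ("To evaluate the safety and tolerability, including local skin tolerability (Dermal Response and Other Effects) of once-weekly" TDS use, SAP 2.3). Protocol Section 3 reports that application-site events made the largest difference between TDS and Aricept in the adverse events of earlier studies. The rule can therefore misplace events of the very kind that separates the treatments.

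**Working it through.** The plan gives no figure on this point, so there is none to reproduce. The check applies the rule to the calendar and then counts the patches exposed to it.

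**Step 1: time from removal to next treatment.** Period 1 to 2: (37 − 36) × 24 = 24 h. Period 2 to 3: (73 − 72) × 24 = 24 h. The 0.5 h check falls before the switch, the 24 h check at it, and the 48 and 72 h checks after it. So do the conditional checks at 120 and 168 h.

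**Step 2: where a reaction with onset after the switch is counted.**

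- ABC, Period 1 to 2 (A to B): a 5 mg site reaction is counted under the 10 mg TDS.
- ACB, Period 1 to 2 (A to C): a 5 mg site reaction is counted under oral Aricept.
- ABC, Period 2 to 3 (B to C): a 10 mg site reaction is counted under oral Aricept.
- ACB, Period 2 to 3 (C to B): no patch precedes the switch, and nothing follows the last 10 mg patch.

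Onset during wear, or on the treatment-free day, is assigned correctly. On Day 36 the special rule does this; on Day 72 the general rule does. A reaction that began before the switch and persists unchanged stays with its patch. One that worsens afterwards is counted under both treatments, provided the data show when it worsened. Protocol 18.1.3 asks only for the maximum severity.

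**Step 3: patches exposed.** Inputs: 48 completers (SAP 4), 5 patches per TDS period (SAP 1), two TDS periods each, and a 1:1 split of ABC and ACB (an assumption).

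- All patches: 48 × 2 × 5 = 480. Fifth patches: 48 × 2 = 96.
- Followed by another treatment: 24 (A to B) + 24 (A to C) + 24 (B to C) = 72, and 72/480 = 15%.
- Of these, 24 + 24 = 48 are followed by oral Aricept and 24 by the other strength.
- With a share f of subjects in ABC, the count is 48 × (1 + f): 67.2 at f = 0.4 and 76.8 at f = 0.6, or 14% to 16%.
- With all 60 enrolled subjects split 1:1, it is 60 + 30 = 90 of 600 (15%): 60 oral and 30 other strength.

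**Step 4: the gap before Period 3.** The addendum's footnote to Listing 16.2.4.6 reports a gap of 7-8 days, or 168 to 192 h, for visits marked as extension days. It does not say how many subjects were affected. If no study drug was given in the gap (an assumption), reactions starting in those days stay with B. Setting aside B to C for every ABC subject, as a limit, leaves 72 − 24 = 48 patches (48/480 = 10%), half followed by oral Aricept and half by the other strength. The Period 1 to 2 switch is unaffected.

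**Step 5: from patches to table entries.** The documents give no rate of reactions with onset more than 24 h after removal, so the number of misassigned events cannot be computed. SAP 6.11.1 counts a subject once per preferred term. The subject count for the TDS that caused the reaction falls only if that subject has no earlier event of the same term on that treatment. Event counts, and the column that receives the event, can still change.

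**The case against.** The strongest counter-argument is that the effect is narrow and partly visible. Only onset or worsening after about 24 h is affected. Protocol Section 3 describes earlier application-site events as largely mild and irritation as decreasing over wear. An application-site term under Aricept has an obvious origin, and all adverse events are listed with study day relative to period start. These points stand and limit the size. They do not make the by-treatment tables correct, and they do not help with A to B.

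A second argument is that local tolerability has its own patch-based analysis (SAP 6.11.7), which this rule does not govern. That also stands, so the objective does not rest on the TEAE tables alone. However, the addendum's footnotes to the skin tolerability tables say that, through an administrative error, only the 0.5 h score was obtained after the Week 5 patch of Treatments A and B. The scores cannot check late reactions at the sites in question.

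A reader might infer more than the documents support:

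- That 15% of local events are misassigned. The figure is a share of patches exposed to the rule.
- That the checks at 120 h and later show late onset. They are made only when a score is already above 1 at 72 h, so they show persistence.
- That every subject passes from patch to oral once. About 60 enrol and 48 are expected to complete.

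**Conclusion.** The concern holds as a defect in a stated attribution rule, and nothing in the SAP, the addendum or Protocol 17.6 corrects it. It touches reactions at the fifth patch's site with onset or worsening after the next treatment starts. About 15% of patches are exposed under the planned calendar, assuming a 1:1 split and 48 completers, and fewer where the Period 3 start was delayed. The misassigned events are probably few. Overall columns, listings and the bioequivalence analysis are not affected. The case for correcting it is that the result is wrong in a table devoted to application-site events and the remedy is cheap.

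**What to change.** Add to SAP 6.11.1, or to a further addendum:

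- A TEAE at a TDS application site, whether by onset or worsening, is assigned to the most recent TDS worn at that site.
- In an oral period it is assigned to the last TDS treatment received before that period; no site link is needed.
- After an A-to-B switch, recorded site information is used where available. Otherwise the chronological assignment is kept and the event is flagged.
- All other TEAEs keep the chronological rule.

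Apply this in Table 14.3.1.8 and the by-treatment TEAE tables, and list the reassigned events. SAP 6 already allows additional tables if the report documents the reason.

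The cost is a small amount of programming and review, and possibly a slightly higher local event count for the TDS. Some A-to-B events may stay unlinked: the adverse event fields in Protocol 18.1.2 do not include the site. Protocol 8.1 also allows a used site to be reused with sponsor approval, which is why the rule names the most recent TDS. Sample size and error rates do not change.

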6.11.2 Laboratory Data

Samples for clinical laboratory tests will be collected at screening, prior to start of Period 1 treatment (Treatment A), at the end of treatment within each study period, and in the event of premature study termination. Descriptive statistics for the the observed values and change from baseline (continuous data) will be presented by treatment for hematology, serum chemistry, coagulation, and urinalysis parameters at the following time points:

- Screening,
- Baseline (last available measurement prior to start of Period 1 treatment),
- End of treatment (Day 36 after TDS application/first dose within study period),
- Early termination (last available sample collected for subjects who prematurely terminated from the study).

Each measurement (continuous data) will be classed as below (low), within (normal), or above (high) normal range, based on ranges supplied by the laboratory used. Shift tables in relation to the normal range from Screening visit to the End of Treatment (EoT) or ET visit will be presented.

A listing of any abnormal laboratory measurements recorded throughout the study will be presented.

All laboratory data, including serology, urine drug screening tests, COVID-19 testing data and pregnancy test data will be listed.

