#### 9.1. Screening Procedures

Subjects will complete the screening visit within 28 days (Day -28 to Day -1) of admission to the in-clinic visit of the Treatment Phase (Day -1). Prior to conducting any study-related activities including screening procedures, written Informed Consent and the Health Insurance Portability and Accountability Act (HIPAA) authorization must be signed and dated by the subject.

The following information collection/assessments will be performed at the Screening Visit:

- 1. Informed Consent and HIPAA authorization by the subject.
- 2. Subject demographics including date of birth, sex, race, and ethnicity.
- 3. Review of inclusion/exclusion criteria to determine study eligibility.
- 4. Record medical history including skin type assessment, chronic conditions, relevant surgical procedures (with start date) history of alcohol and recreational drug use, smoking status, evaluation of drug and alcohol use and personal habits affecting the skin (example: tanning, hair removal, and application of tattoos).
- 5. Fitzpatrick skin type score: Type I always burns, never tans, Type II usually burns, tans with difficulty, or Type III may burn initially, but tans easily.
- 6. A complete physical examination with back evaluation and personal habits affecting the skin (example: tanning, hair removal, and application of tattoos).
- 7. Body weight, height, and BMI.
- 8. Vital signs after a minimum of 3 minutes of rest (respiratory rate, pulse rate, blood pressure, and oral temperature).
- 9. 12-lead electrocardiogram (ECG) after subject has been in supine position for a minimum of 3 minutes. Abnormal ECGs may be repeated for confirmation in which case only the repeated ECG will be recorded. The QT interval corrected for heart rate will be calculated with Fridericia's formula (QTcF).

- 10. Clinical laboratory tests (chemistry, hematology, coagulation, and urinalysis) obtained under fasted conditions. During the Screening Period, Clinical Laboratory Measurements may be repeated at the discretion of the Investigator.
- 11. Blood samples for Serology (HIV antibody, hepatitis B surface antigen and hepatitis C virus antibody).
- 12. Urine samples will be tested for alcohol, drugs of abuse (amphetamines, methamphetamines, benzodiazepines, barbiturates, cannabinoids, cocaine, and opioids) If the test is positive for any of the tested analytes, the subject will be excluded from study participation.

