6.2.2 Baseline

For variables that will be summarized by treatment, the baseline for each period is defined as the last non-missing value (either scheduled, unscheduled or repeat) that is collected before dosing, in the relevant period.

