6.2.7 Unscheduled Visits

Only scheduled post-baseline laboratory and vital signs values will be tabulated. Post-baseline repeat/unscheduled assessments will not be included in summary statistics. However, these repeat/unscheduled post-baseline assessments will be included in the relevant listings.

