6.11.4 Electrocardiogram Data

Twelve-lead electrocardiograms (ECGs) will be obtained at screening, prior to start of Period 1 treatment (Treatment A), and at the end of treatment (Day 109). Additionally, ECGs will be obtained in the event of premature study termination. Descriptive statistics for observed values and changes from baseline in the following ECG variables will be tabulated overall at the end of treatment (Study Day 109):

- Heart rate (bpm)
- PR interval (ms)
- RR interval (ms)
- QRS duration (ms)
- QT interval (ms)
- QTcB interval (ms) [Bazett's formula]
- QTcF interval (ms) [Fridericia's formula]

If an ECG measurement was repeated, only the repeated measurement was recorded.

Shift tables in relation to the overall interpretation (Normal, Abnormal NCS, and Abnormal CS) from baseline to end of treatment (Study Day 109) will be presented.

All ECG data, including details of any abnormalities, will be listed.

Page 36 of 61 Confidential

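### Laboratory shift tables start at Screening rather than at the pre-dose baseline, so they flag some changes that preceded the first dose and miss some that followed it

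*SAP*

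**What the plan says.** SAP 6.11.2 classes each continuous laboratory value as low, normal or high and then states: "Shift tables in relation to the normal range from Screening visit to the End of Treatment (EoT) or ET visit will be presented". In the same section, the time points for observed values and change from baseline include "Baseline (last available measurement prior to start of Period 1 treatment"). Protocol 9.2 and 12.6 schedule a laboratory draw on Day -1, so that baseline will normally be the Day -1 sample. Screening may take place up to 28 days before admission (Protocol 9.1).

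Three other places bear on the point:

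- SAP 6.11.4 runs the ECG shift table "from baseline to end of treatment (Study Day 109) will be presented".
- SAP 6.2.2 gives a different, period-specific rule for by-treatment summaries: "the baseline for each period is defined as the last non-missing value (either scheduled, unscheduled or repeat) that is collected before dosing".
- SAP 6.2.7 limits the post-baseline summaries: "Only scheduled post-baseline laboratory and vital signs values will be tabulated".

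Protocol 17.6 plans laboratory summaries as change from baseline. It does not mention laboratory shift tables.

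**The concern.** A shift table should show who moved out of the normal range after treatment began. If it starts at Screening, the interval it covers includes the untreated weeks before Day 1. Two kinds of subject are then misplaced. One was normal at Screening, already abnormal on Day -1 and still abnormal at end of treatment; this subject appears as normal-to-abnormal although the change came before any drug. The other was abnormal at Screening, normal on Day -1 and abnormal on drug; this subject appears as abnormal-to-abnormal, and the on-treatment change is hidden.

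The change-from-baseline table and the shift table for the same analyte (for hematology, Tables 14.3.7.1 and 14.3.7.2) would also use different starting points and could disagree about the same subject. The SAP gives no reason for the choice. Safety and tolerability are a stated objective (Protocol 5.3), and the shift tables are the categorical laboratory summary in the SAP's table list.

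**Working it through.** **Text check.**

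| Output | Starting point | Where |
|---|---|---|
| Laboratory change from baseline | Last value before Period 1 treatment | SAP 6.11.2 |
| Laboratory shift tables | Screening | SAP 6.11.2 |
| ECG shift table | Baseline | SAP 6.11.4 |
| Any variable summarized by treatment | Last value before dosing in that period | SAP 6.2.2 |

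The laboratory shift tables are the only one of these outputs that starts at Screening. The Day -1 sample needed for a pre-dose start is already scheduled.

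**Size.** The plan has no figure to reproduce, so this is an illustration on assumed inputs. For one analyte, let the values at Screening (S), Day -1 (D) and end of treatment (E) be standard normal with a common correlation ρ:

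X = √ρ · B + √(1 − ρ) · e,

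with B shared within a subject and e independent between visits. There is no drug effect. The reference range is the central 95%, so high means X > 1.96. The scale is 60 subjects, the planned enrolment (SAP 4). The share of tabulated shifts already present before dosing is

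P(S normal, D high, E high) / P(S normal, E high).

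Simulation with 4 million draws gives the following expected normal-to-high shifts per analyte per 60 subjects:

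| ρ | Counted from Screening | Counted from Day -1 | Of the Screening count, already high on Day -1 | Share |
|---|---|---|---|---|
| 0.5 | 1.22 | 1.22 | 0.18 | 15% |
| 0.7 | 1.00 | 1.00 | 0.23 | 23% |
| 0.9 | 0.62 | 0.61 | 0.22 | 35% |

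Direct numerical integration gives the same shares to the nearest percent, both for normal-to-high and for normal-to-abnormal in either direction.

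**Missed shifts.** With one common correlation, Screening and Day -1 are interchangeable in the model. The share of true shifts from Day -1 that is lost because Screening was abnormal is therefore the same 15% to 35%. This is why the first two count columns agree: the two errors cancel in the total but concern different subjects.

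**Over the panel.** Protocol 12.6 lists 10 hematology, 2 coagulation and 19 chemistry analytes, which makes 31. With 55 subjects (the SAP 6.12 expectation for the 5 mg/day TDS) there are 55 × 31 = 1,705 subject-analyte cells per treatment. For ρ of 0.55 to 0.7, about 67 to 57 cells show a normal-to-abnormal shift from Screening. Of these, 17% to 23%, or about 11 to 13 cells, were already abnormal on Day -1.

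**If only subjects normal at Screening are enrolled.** The counts from Screening and from Day -1 become 1.28 and 1.09 (ρ = 0.5), 1.05 and 0.81 (ρ = 0.7), and 0.65 and 0.42 (ρ = 0.9). The excess is (1.28 − 1.09)/1.28 = 15%, (1.05 − 0.81)/1.05 = 23% and (0.65 − 0.42)/0.65 = 35%. The share is unchanged, because it already conditions on a normal Screening value. In that case, however, the total is inflated and there are no missed shifts.

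**The case against.** The strongest reply is that this is a one-line inconsistency in a descriptive table. Protocol 17.6 promises change from baseline and listings of significant abnormalities, and SAP 6.11.2 delivers both. Every Day -1 value is listed, and no decision rule uses the shift tables. This stands and limits the importance of the point. It does not make Screening the right reference.

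A second reply is that the SAP has no single pre-dose baseline to substitute: 6.2.2 is period-specific, while 6.11.2 uses one value before Period 1. This stands and changes the remedy. With a single pre-Period 1 reference shown by treatment, an abnormality that arose under Treatment A and persisted would be counted again under B or C.

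Three stronger readings are tempting but not supported:

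- *That transient on-drug abnormalities never count, because 6.2.7 excludes unscheduled values.* Abnormalities present at the scheduled Day 36, 72 or 109 draws can enter the tables. For unscheduled values, "these repeat/unscheduled post-baseline assessments will be included in the relevant listings". SAP 6.11.2 adds: "A listing of any abnormal laboratory measurements recorded throughout the study will be presented". An abnormal laboratory finding can also be an adverse event (Protocol 18.1.2). All that remains is that an abnormality seen only at an unscheduled draw stays out of the shift tables.
- *That Screening values are selected to be normal across the panel.* Protocol 9.1 does allow retesting: "During the Screening Period, Clinical Laboratory Measurements may be repeated at the discretion of the Investigator". Numeric exclusion limits, however, cover only ALT, AST and estimated creatinine clearance (Protocol 7.2.2), and an isolated ALT or AST above normal but below 1.5 times the upper limit is admitted. Other findings exclude only if judged clinically significant. Repeating until normal could raise the share, but nothing in the documents allows that to be quantified.
- *That fasting status favours Day -1.* Screening is fasted (Protocol 9.1) and the Day 109 sample need not be (9.4.5), but 9.2 does not specify fasting on Day -1.

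**Conclusion.** The point holds as a mismatch of reference visit. Followed as written, SAP 6.11.2 counts some pre-dose changes as shifts and misses some that began on treatment. The mismatch is certain from the text. Its size is not: roughly 15% to 35% in each direction depends on an assumed central 95% range, no drug effect and one common correlation between 0.5 and 0.9. Unequal correlations would make the two shares differ. The documents do not support a claim that total shifts are generally inflated; that follows only to the extent that subjects were selected as normal at Screening. The consequence is confined to descriptive safety tables. The correction is worth making because it is nearly free, but it does not touch the bioequivalence conclusion.

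**What to change.** In SAP 6.11.2:

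1. Replace the Screening visit with the pre-dose baseline as the start of the shift tables.
2. Reconcile this section with 6.2.2. For shifts shown by treatment, use the period-specific value: normally Day -1 for Period 1, and the last value before dosing in Periods 2 and 3 (the scheduled draws on Study Days 36 and 72). A shift that arose under Treatment A and persists is then not counted again under B or C.
3. State that end of treatment is Day 36 of each period, and name the study days: 36, 72 and 108/109. The last needs settling, because Day 36 of Period 3 is Study Day 108, while Protocol 12.6 and 9.4.5 place the draw on Day 109.

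Optionally, add a shift to the worst post-baseline value in the period, including unscheduled draws, as a stated exception to 6.2.7. Those values are already listed, and the main correction does not depend on this table.

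The cost is a few sentences and a changed reference variable in the shift-table program. No new data are needed.
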